## **8. Possible Benefits:**

There is no direct benefit to the participant.

## **9. Conflict of Interest:**

None.

## **10. Statistical Analysis Plan**

This is an R21 study that is designed to acquire data for planning a full scale clinical trial. Summary statistics will be provided for all primary measures, as well as for demographic and clinical characteristics. For the primary outcome of each hypothesis, group mean differences and standard deviations will be used to calculate effect sizes. With this information we will be able to conduct a power analyses to plan for a future full-scale clinical trial.

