### 3. Abstract:

Loss of mobility and cognitive ability are serious conditions that threaten the independence of older adults. Importantly, both of these conditions are mechanistically linked by impairment of frontal lobe brain function. Frontal lobe dysfunction has been implicated as a factor contributing to gait deficits in some individuals with Alzheimer's disease, frontotemporal dementia and vascular dementia. There is a critical gap in knowledge about what therapeutic strategies are effective for maintaining or reinstating function in this critical brain region in order to preserve physical and cognitive health in older adults. The goal of our research is to develop a novel therapeutic intervention to enhance both mobility and cognition via neuroplasticity of frontal/executive control circuits. We will engage neuroplasticity of frontal circuits in two ways. The first is through neurorehabilitation with "complex walking tasks" (CWTs), such as obstacle crossing, obstacle avoidance and walking on non-uniform surfaces. CWTs are a potent behavioral approach for engaging prefrontal circuits. Furthermore, CWTs are crucial to successful ambulation in the home and community settings and therefore provide an ecologically valid therapeutic approach. The second approach that we will use to engage neuroplasticity of frontal circuits is anodal transcranial direct current stimulation (tDCS). Anodal tDCS is a safe, non-invasive neuromodulation technique. It has previously been shown to induce excitatory effects on brain tissue and, in single-session assessments, to improve performance during complex walking tasks. tDCS has also been shown to be an effective adjuvant for enhancing the effects of cognitive training. The objective of this study is to calculate effect size, establish variance of response and demonstrate feasibility of the experimental interventions in order to plan for a full scale clinical trial. Participants will include thirty older adults who demonstrate evidence of frontal/executive impairment. Participants will be randomized to one of three groups: 1) standard walking neurorehabilitation with sham tDCS ('standard/sham' group), 2) complex walking neurorehabilitation with sham tDCS ('complex/sham' group), or 3) complex walking neurorehabilitation with active anodal tDCS ('complex/active' group). Functional near infrared spectroscopy (fNIRS) will be used to explore intervention-induced changes in prefrontal cortical activity. Assessments will be conducted at baseline, post-treatment and 3-month follow up. We propose the following specific aims:  

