**5. Specific Aims:**

**Specific Aim 1: Determine preliminary efficacy for recovery of mobility and cognitive function.**

Primary Mobility Outcome: Figure-of-eight walking test (Figure-8 Walk Test)

Primary Cognitive Outcome: Composite executive score on NIH EXAMINER battery (EXAMINER)

Hypothesis 1a: Effect sizes for improvement in the *Figure-8 Walk Test* will be greatest for *complex/active*, followed by *complex/sham*, followed by *standard/sham*.

Hypothesis 1b: Effect sizes for improvement on EXAMINER will be greatest for *complex/active*, followed by *complex/sham*, followed by *standard/sham*.

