## **6. Research Plan:**

### Study Overview

All study procedures will be conducted at the University of Florida.

Up to thirty older men and women will be enrolled in the intervention component of this study. A larger number will be enrolled for onsite screening, because some will fail the screening tests and not proceed to the study intervention. Volunteers will undergo the following sequence of events:

- *Telephone Screening*: Volunteers will be screened by telephone to determine if they meet basic enrollment criteria including age and general health status.
- *1st Informed Consent and Onsite Screening*: Volunteers who pass the phone screen will be invited to participate in on-site screening. Informed consent for screening will be obtained. Mobility function and cognitive screening will be conducted, including 10m walk speed and tests from the cognitive battery of the NIH Toolbox. Other criteria listed in Table 6 will also be evaluated. Screening will be conducted over two visits lasting approximately 4 hours and 3 hours, respectively. A third visit may sometimes be needed if all assessments cannot be completed in the two visits
- *2nd Informed Consent and Baseline Assessment*: Qualifying volunteers will be invited to participate in the full study. They will attend a baseline assessment session which will include Informed Consent for full study participation and tests of the primary and secondary study outcomes including Figure-8 walk test and NIH EXAMINER battery of executive function. Secondary outcomes will also be evaluated as described in the Research Plan. This visit will last approximately 3 hours.
- *Rehabilitation Intervention*: Enrolled participants will receive 18 sessions of neurorehabilitation, which will be combined with either active or sham tDCS. These sessions will be completed over the course of 6 weeks. Each session will last about 75 minutes from arrival to departure.
- *Post-Intervention Assessment*: At the completion of the neurorehabilitation program, participants will attend a post-therapy assessment session that is identical to the baseline assessment.
- *Three month follow up Assessment*: Three months after completing the neurorehabilitation program, participants will attend a 3-month follow up assessment session that is identical to the baseline and post-treatment assessments.

---

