### **Rehabilitation Intervention**

Participants will take part in a 6-week, 18-session neurorehabilitation led by qualified and trained study personnel. Participants will be randomized to one of three groups: 1) standard walking neurorehabilitation with sham tDCS ('standard/sham' group), 2) complex walking neurorehabilitation with sham tDCS ('complex/sham' group), or 3) complex walking neurorehabilitation with active anodal tDCS ('complex/active' group). Training logs will be maintained to gauge the content and intensity of training. To control for intensity, participants will maintain a rating of perceived exertion of 4 (moderate to strong) on the Borg Category/Ratio Scale during walking. Exertion will be adjusted by modifying walking speed and/or by modifying the rest time between walking bouts. Training logs will also include information on attendance and adverse events. From these logs we will determine adherence (# of sessions attended), retention (completion of rehabilitation and post-therapy assessment) and number of adverse events.

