#### **Post-Intervention Assessment and 3-Month Follow-Up Assessment**

The procedures will be identical to what is described for the baseline assessment

---

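### Aim 1 effect sizes rest on unadjusted group means and an unnamed SD, although both primary outcomes are measured at baseline in every participant

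*Combined protocol and SAP*

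**What the plan says.** The Abstract sets out what the study is to deliver: "The objective of this study is to calculate effect size, establish variance of response and demonstrate feasibility of the experimental interventions". Section 10 (Statistical Analysis Plan) promises descriptive summaries and then gives the only analysis method for Aim 1: "For the primary outcome of each hypothesis, group mean differences and standard deviations will be used to calculate effect sizes". It continues: "With this information we will be able to conduct a power analyses to plan for a future full-scale clinical trial". No model, covariate, score type, visit or standardising SD is named there or elsewhere.

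Section 5 words the two Aim 1 hypotheses in terms of improvement, for example "Effect sizes for improvement on EXAMINER will be greatest for" the complex/active arm. This makes change from baseline the likelier reading, but no change score is defined.

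The Study Overview in section 6 places at the baseline session "tests of the primary and secondary study outcomes including Figure-8 walk test and NIH EXAMINER battery of executive function". For the post-intervention and 3-month visits the plan states: "The procedures will be identical to what is described for the baseline assessment". On size and design it says "Up to thirty older men and women will be enrolled in the intervention component of this study" and "Participants will be randomized to one of three groups". It gives no allocation ratio.

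**The concern.** With about ten people per arm, chance differences between arms at baseline will be common. An unadjusted contrast carries part of any such difference into the estimated effect, whether it uses change scores or follow-up scores. The baseline score that would remove this is already planned for everyone, and the plan does not use it as a covariate.

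The divisor is also undefined. The same treatment difference gives a different standardised effect when divided by the SD of raw scores, of change scores, or of residuals after baseline adjustment. An effect size reported without its SD can be paired with the wrong analysis when the full-scale trial is sized. Producing that effect size is the purpose of this study, so calling it a planning study does not remove the problem.

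**Working it through.** The plan states no power, alpha or derived sample size, so there is no figure of its own to reproduce.

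**Inputs.** From the documents: up to 30 participants and three arms. Assumed, because the documents give none: 10 per arm, equal SDs (set to 1) at both visits, normal scores, randomisation not stratified on the outcome, and r from 0.5 to 0.9. For sizing the next trial: two-sided 5% and 80% power.

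**1. Chance imbalance.** The SD of a baseline difference between two arms is √(2/10) = 0.447. P(|difference| > 0.5 SD) = 2[1 − Φ(0.5/0.447)] = 0.26 for a given pair. By simulation it is 0.50 for at least one of the three pairs. With 8 per arm the figures are 0.32 and 0.58.

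**2. What each contrast does with it.** For a baseline difference D, the change-score contrast carries −(1 − r)D, the follow-up-only contrast +rD, and ANCOVA about zero. Simulated slopes at r = 0.7 were −0.30, +0.70 and 0.00. With D = 0.5 SD the absolute shifts are:
- change score: 0.25, 0.15 and 0.10 SD at r = 0.5, 0.7 and 0.8;
- follow-up only: 0.25, 0.35 and 0.40 SD.

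**3. Precision.** The variance of a contrast is proportional to 1 (follow-up only), 2(1 − r) (change) and (1 − r²)(1 + 1/25) (ANCOVA). The last factor is the cost of estimating the slope, with 25 = 30 − 3 − 2. So ANCOVA/change = 1.04(1 + r)/2, which reaches 1 at r = 2/1.04 − 1 = 0.92. ANCOVA/follow-up at r = 0.7 is 1.04 × 0.51 = 0.53.

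**4. Choice of SD.** Take a true difference of 0.5 raw SD. Then d = 0.5 on the raw SD, 0.5/√(2(1 − r)) on the change SD, and 0.5/√(1 − r²) on the residual SD. The number per arm is 2(1.960 + 0.842)²/d², rounded up.

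| r | ANCOVA/change variance | SE reduction | d: raw, change, residual | n per arm: raw, change, residual |
|---|---|---|---|---|
| 0.5 | 0.780 | 12% | 0.50, 0.50, 0.58 | 63, 63, 48 |
| 0.7 | 0.884 | 6% | 0.50, 0.65, 0.70 | 63, 38, 33 |
| 0.8 | 0.936 | 3% | 0.50, 0.79, 0.83 | 63, 26, 23 |
| 0.9 | 0.988 | 1% | 0.50, 1.12, 1.15 | 63, 13, 12 |

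Simulation of 100,000 trials gave variance ratios of 0.782, 0.882 and 0.934 at r = 0.5, 0.7 and 0.8.

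**5. Consequence of a mismatch.** Suppose the next trial is sized at 38 per arm from the change-score d at r = 0.7 but compares follow-up scores alone. Its power is Φ(0.5 × √(38/2) − 1.96) = Φ(0.22) = 0.59.

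**The case against.** On the likelier reading, change scores already use the baseline. ANCOVA then shortens the SE by only 6% at r = 0.7 and 1% at r = 0.9. In 95% half-widths that is 0.71 against 0.67 SD at r = 0.7. Sampling error is far larger: at 10 per arm, d = 0.5 has SE √(2/10 + 0.5²/40) = 0.454 and a 95% CI of about −0.39 to 1.39. **This stands.** It limits the weight of the adjustment argument and is a reason to report intervals, but it gives no reason to leave a free gain unused.

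The words on improvement in section 5 and on variance of response in the Abstract may together point to the SD of change. If visit-wise SDs s₁ and s₂ are also reported with the change SD s_d, then r = (s₁² + s₂² − s_d²)/(2s₁s₂), and the next trial could be sized for any analysis. **This stands in part.** The plan commits to neither the change SD nor visit-wise SDs, and visit-wise SDs alone do not yield r.

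The hypotheses could also mean one pre-to-post effect size per arm, ranked across arms. That is possible, but the full-scale trial still needs a between-arm contrast, and that contrast would remain unadjusted.

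Equal SDs may fail, because the screening criteria select slow walkers with below-median executive scores, which could compress baseline variance. This is fair, and it is a reason to report each SD separately. The 59% power figure is conditional: nothing in the plan says that mismatch will occur.

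**Conclusion.** The concern holds. Section 10 derives the Aim 1 effect sizes from unadjusted means and does not define the score type, the visit or the divisor. A better estimator is available from data already scheduled. The precision gain over change scores is modest (variance 0.78 to 0.99 for r from 0.5 to 0.9, and none above about 0.92). It is large if follow-up scores alone are meant (0.53 at r = 0.7). The undefined SD has the larger consequence: 63, 38 or 33 per arm for the same true difference at r = 0.7, and 63, 26 or 23 at r = 0.8.

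Under randomisation this is chance error and loss of precision in the one sample obtained, without systematic bias. No stated figure in the plan is wrong, and the gap does not invalidate the study. It should nevertheless be closed. The sizes depend on the assumed r, equal allocation and equal SDs.

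**What to change.** Amend section 10 as follows.

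- For each primary outcome, estimate the between-arm differences by ANCOVA of the post-intervention score on arm, with that outcome's baseline score as covariate, and give 95% CIs. Repeat separately for the 3-month score, and state which visit supplies the planning effect size.
- Standardise the adjusted difference by a named SD, for example the pooled baseline SD.
- Report the raw SD at each visit, the change SD, the residual SD, and the baseline-to-follow-up correlation with its 95% CI. With r = 0.7 in 30 people that interval is tanh(0.867 ± 1.96/√27), about 0.45 to 0.85.
- If per-arm pre-to-post effect sizes are wanted, report them as descriptive, in addition to the between-arm contrasts.
- Size the full-scale trial with the SD that matches its own analysis, over that range of r.

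The cost is SAP wording and one degree of freedom per outcome. No extra visits or data are needed.

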## **Data and Safety Monitoring Plan**

### ***Data Safety Monitoring Board***

This study will use the Pepper Safety Committee for data and safety monitoring. This committee, henceforth called the Data Safety Monitoring Board (DSMB) is used for most studies that are affiliated with the UF Claude Pepper Older Americans Independence Center. The three members of this committee have no affiliation with the study. The committee meets every 6 months.

The PI will provide the DSMB with access to all relevant study data, documents and progress information. The PI and designated staff will attend the DSMB meetings and will be responsible for preparing and presenting data reports from the study.

The DSMB has the following charges:

- The initial task of the DSMB is to review the study protocol with regard to recruitment, randomization, intervention, subject safety, data management, plans for auditing of subject records, quality control and analysis plans, and to identify needed modifications. The DSMB then identifies the relevant data parameters and the format of the information to be regularly reported.
- Review data over the course of the trial relating to recruitment, randomization, compliance, retention, protocol adherence, trial operating procedures, forms completion, intervention effects, gender and ethnic/racial minority inclusion and subject safety.

- Identify problems relating to safety over the course of the study. Inform study PI via written report.
- Identify needs for additional data relevant to safety issues and request these data from the study investigators.
- Propose appropriate analyses and periodically review developing data on safety and endpoints.
- Make recommendations regarding recruitment, treatment effects, retention, compliance, safety issues and continuation of the study.
- Send the Program Administrator and PI written reports following each DSMB meeting. These reports may address all issues reviewed by the DSMB.
- The study PI is responsible for distributing the report to the local IRB.

The DSMB may convene an executive session at any time. The PI, project director, and project officer would attend these meetings. Any additional requirements pertaining to the DSMB will be determined by the NIA.

### ***Adverse Event Reporting***

Adverse events (including expected, unexpected, serious and non-serious) will be tracked in a cumulative table. Adverse events will be reported according to the guidelines of the University of Florida Institutional Review. Specifically, adverse events that are serious and unexpected (see definitions below) will be reported to the UF IRB within 5 working days of when study personnel learned about it. Reports of adverse events that are not serious or that are expected (e.g., muscle soreness) will be added to the cumulative adverse event table and reported to the UF IRB annually.

A *serious adverse event* is any adverse event that results in any of the following outcomes:

- death,
- a life-threatening adverse event,
- inpatient hospitalization or prolonging existing hospitalization,
- a persistent or significant disability/incapacity,
- or a congenital anomaly/birth defect.

Important medical events that may not result in death, be life-threatening, or require hospitalization may be considered a serious adverse event when the event may jeopardize the patient or subject and/or may require medical or surgical intervention to prevent one of the outcomes listed in the definition above.

An *unexpected adverse event* is any adverse event that is not consistent with the current investigator brochure, protocol, consent form, or is not part of the normal disease progression. In addition, known adverse events may occur more frequently than expected. If so, then this meets the definition of “unexpected” and must be reported to the IRB.

### ***Protection Against Risk***

Staff training: All personnel will be thoroughly trained in the study procedures by the Principal Investigator or other appropriate member of the research team, and will complete all required trainings concerning human subjects research at the University of Florida. Personnel involved with administering tDCS will be trained in the lab of [name], who has extensive experience with this technology.

Health monitoring and medical response: Volunteers at risk of health problems due to recent history of medical conditions (e.g., serious cardiac or pulmonary conditions) will be excluded, as noted above in the inclusion/exclusion criteria. Any adverse events will be recorded and monitored as required by our University of Florida Institutional Review Board. On-site medical

services will be available in the event of adverse events occurring during screening or assessment visits. Subjects will be able to terminate a study session at their request at any time without prejudice. Minimization of risk during neurorehabilitation and assessments will be accomplished by monitoring vital signs, with prescribed criteria for termination of the testing session. Vital signs will be monitored before, during and after assessment. Contraindications for participation will include resting heart rate >100 bpm or <50 bpm, resting systolic blood pressure >180 mmHg or <100 mm Hg or resting diastolic blood pressure >100 mmHg. Indications to terminate physical activity will include heart rate that exceeds age-predicted maximum (220-age), sudden drop in heart rate exceeding 15 bpm, systolic blood pressure >220 mmHg or <100 mmHg, or diastolic blood pressure >110 mmHg. Other criteria for termination include subject complaints of shortness of breath, light-headedness, dizziness, confusion, severe headache, dyspnea or onset of angina. Should the session be halted, the subject will be asked to rest while BP and HR are monitored and will resume only if BP and HR return to acceptable values. If any of these conditions persist after rest, the patient's primary physician will be called and patient referred for evaluation. If the patient complains of angina at rest, loss of consciousness occurs, or cardiac arrest, emergency medical services through 911 will be called immediately. Portable defibrillators will be available.

Confidentiality: Data will be used only in aggregate and no identifying characteristics of individuals will be published or presented. Confidentiality of data will be maintained by using research identification numbers that uniquely identify each individual. Safeguards will be established to ensure the security and privacy of participants' study records. Appropriate measures will be taken to prevent unauthorized use of study information. Data other than demographic information will not use names as an identifier. The research ID number will be used. The research records will be kept in a locked room in the study site. The files matching participants' names and demographic information with research ID numbers will be kept in a locked file that uses a different key from that of all other files. Only trained and certified study personnel will have access to these files, and they will be asked to sign a document that they agree to maintain the confidentiality of the information. Electronic records will be stored on password protected network server maintained by the university information technology department. In compliance with the Health Insurance Portability and Accountability Act (HIPAA) and the Standards for Privacy of Individually Identifiable Health Information of the Department of Health and Human Services, we access personal health information and medical records only after receiving signed informed consent.

Safety during neurorehabilitation: Neurorehabilitation sessions will be led by a licensed physical therapist or other qualified staff member assigned by the Principal Investigator. The intensity and duration of walking activity will be carefully monitored to ensure that it is appropriate to the participant's capabilities. Participants will wear a gait belt during neurorehabilitation, which will better enable the therapist and/or assistants to provide support in the event of a loss of balance. Falls or near-falls during neurorehabilitation will be tracked on the therapy log and reported to the PI and DSMB.

tDCS Safety: Our protocol uses stimulation parameters that are considered standard practice, and have been used safely in prior research. The FDA has ruled that the tDCS stimulator used in this study is a "non-significant risk" device. The most common side effects of tDCS are slight itching, tingling, and reddening of the skin under the electrode. Participants typically habituate to itching or tingling sensations within 60 seconds of stimulation. Less common symptoms of stimulation are headache or nausea. Both headache and nausea have been reported to stop when stimulation is terminated. To minimize risk associated with tDCS, participants will be monitored throughout stimulation sessions and asked to report any discomfort. If scalp sensation is uncomfortable, stimulation levels will be decreased to a comfortable level or will be

stopped. In the event of a headache, stimulation will be decreased to a comfortable level (where the headache or nausea is no longer present) or will be stopped. All tDCS sessions will be administered and continually supervised by a trained experimenter.

**fNIRS Safety:** fNIRS poses no safety risk. Infrared light from the fNIRS device is not harmful and elicits no sensation. Sensors may be secured to the skin using adhesive tape, which could lead to mild skin irritation in those who are sensitive to adhesives. If a person indicates or displays such a sensitivity, we will avoid using adhesive tape and instead use elastic fabric or straps to secure the sensors.

**Questionnaire administration:** Questionnaire data are collected in secure spaces where the interview cannot be overheard. Participants will be informed that they are not required to answer questions that they do not wish to answer.

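### Exertional angina that clears with rest requires no medical evaluation before the participant walks again

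*Combined protocol and SAP*

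**What the plan says.** The relevant rules are in the health monitoring paragraph of Protection Against Risk, within the Data and Safety Monitoring Plan.

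- **Stopping.** Besides heart rate and blood pressure limits, activity is stopped for complaints of "shortness of breath, light-headedness, dizziness, confusion, severe headache, dyspnea or onset of angina".
- **Resuming.** One rule covers every halt. The participant is "asked to rest while BP and HR are monitored and will resume only if BP and HR return to acceptable values".
- **Referral.** "If any of these conditions persist after rest, the patient's primary physician will be called and patient referred for evaluation".
- **Emergency call.** "If the patient complains of angina at rest, loss of consciousness occurs, or cardiac arrest, emergency medical services through 911 will be called immediately".
- **Contraindications.** The list opens with "Contraindications for participation will include resting heart rate" and otherwise contains only resting blood pressure limits.
- **Stated intent on cardiac risk.** "Volunteers at risk of health problems due to recent history of medical conditions (e.g., serious cardiac or pulmonary conditions) will be excluded". Telephone Screening also requires that volunteers have no current cardiovascular disease, and those questions are repeated at onsite screening.

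**The concern.** Angina is treated as serious enough to stop a session. Once it has gone, the only written test for walking again is whether heart rate and blood pressure are acceptable. Normal vital signs do not show what caused the angina.

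This sits badly with the trial's own entry rules. New angina on exertion raises the question whether the participant has current cardiovascular disease, which would have kept that person out at screening. The plan states no re-check of eligibility after such an event. Participants are over 65 and train at a perceived exertion of 4, described as moderate to strong (Rehabilitation Intervention). Staff could follow every written rule and have the participant train again, that day or at the next session, without a physician having been contacted.

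**Working it through.** There is no figure to reproduce and no arithmetic to do. The check is to follow one case through the written rules: angina comes on while walking, stops during rest, and heart rate and blood pressure return to acceptable values.

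| Step | Condition in Protection Against Risk | Met in this case? | Result |
|---|---|---|---|
| 1. Stop activity | Onset of angina | Yes | Session halted, participant rests |
| 2. Resume | Heart rate and blood pressure acceptable | Yes | Resumption permitted |
| 3. Call physician, refer | Condition persists after rest | No, it has settled | No referral required |
| 4. Call 911 | Angina at rest, loss of consciousness or cardiac arrest | No, it came with effort and has gone | No call required |
| 5. Take part in a later session | Resting heart rate and blood pressure within limits | Yes, if vital signs are normal that day | No bar to training |

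Two points of wording bear on the trace.

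- The section speaks of terminating activity, which could be read as ending the session. The resume sentence follows directly, applies to any halted session and does not exempt angina. Even if the session did end, step 5 would still allow the next one without evaluation.
- The phrase *only if* makes acceptable vital signs a necessary condition. It permits resumption and does not direct it. No second condition is written, either of symptom type or of medical clearance.

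The rest of the protocol was then checked for a rule that would require evaluation.

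- **Exclusion criteria.** The Principal Investigator may declare anyone ineligible to continue if participation may be unsafe. This is a discretion, and no evaluation is required.
- **Rehabilitation Intervention, Adverse Event Reporting and Protection Against Risk.** Adverse events go on the training log and in a cumulative table, and "Any adverse events will be recorded and monitored as required by our University of Florida Institutional Review Board". This is recording and oversight, not clearance.
- **On-site medical services.** Protection Against Risk states these for screening and assessment visits. Training sessions are not mentioned, and use of the services is not made a condition of resuming.
- **Safety during neurorehabilitation.** Falls and near-falls must be reported to the Principal Investigator and the DSMB. There is no matching line for angina.

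None of these requires evaluation before the participant walks again.

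**The case against.** The strongest answer is that little is left uncovered, and that what is left lies in competent hands. Angina still felt while the halted participant rests can be read as meeting the 911 rule at once. If *at rest* is taken to mean only spontaneous angina, pain that continues still triggers the physician call and referral. Sessions are led by a licensed physical therapist or other qualified staff member, the Principal Investigator can stop anyone, and "Portable defibrillators will be available". On-site medical services cover the screening and assessment visits. The DSMB reviews the protocol for subject safety at the outset and may convene at any time. Important medical events that may jeopardize a participant can be classed as serious. Current cardiovascular disease, and myocardial infarction or major heart surgery in the previous year, are screened out. Harm would need angina in a screened participant, complete settling, and a decision by staff to carry on.

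Most of this stands, and it limits the point to angina that fully clears. It does not close the gap. Each safeguard is optional, acts after the event, or is not stated for training sessions.

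A reader might infer three stronger things that the documents do not support:

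- **That staff are told to resume.** They are not; the wording sets a minimum condition.
- **That a participant still in pain may walk on once vital signs are acceptable.** The persist-after-rest rule and the 911 rule cover that participant.
- **That the IRB reporting times or the DSMB's six-monthly meetings measure the risk.** Those are oversight intervals. Whether one participant walks at the next session is decided by session staff and the Principal Investigator.

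**Conclusion.** The point holds in a limited form. Followed exactly, the written rules allow a participant whose exertional angina has cleared to walk again, in the same or a later session, without medical evaluation. This goes beyond missing detail, because a stated rule permits the step and it conflicts with the trial's own cardiovascular exclusion.

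No numerical size can be given. The documents contain no rate of angina, and with up to thirty participants the event may never occur. No estimand, analysis or sample size is affected. The conclusion rests on two assumptions: that the resume sentence applies to every listed reason for a halt, as its wording indicates, and the clinical judgement that new exertional angina warrants evaluation even when it settles. This is a cheap improvement to safety wording.

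**What to change.** Add one sentence directly after the resume sentence in Protection Against Risk:

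> A participant halted for angina does not resume that session even if the angina, BP and HR settle; the Principal Investigator is told the same day, the primary physician is called, and no further training or walking assessment takes place until medical clearance is received.

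The rules for other symptoms, and the overlap between the referral and 911 rules, can stay as they are: changing them would only restate or tidy what the text already implies.

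The cost is that an affected participant may miss sessions while awaiting clearance. Adherence is counted as sessions attended, so that person's count under Aim 2 would fall.
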